- 1.5. To evaluate fatigue upon application of Neo-Russian, Aussie and RBS currents by means of a fatigue test with isometric dynamometry in healthy subjects from 18 to 30 years of age.
- 1.6. To compare the fatigue induced by the different currents in healthy subjects between 18 and 30 years of age in order to determine which of the three produces less fatigue.

MATERIALS AND METHODS

a. Design type

Experimental, crossover, randomized study (45).

b. Location

The data collection was carried out in the "*[name] Terapia Física Especializada*" Center, located at [name], in the Autonomous City of Buenos Aires, Argentina, in the period from 11-30-2017 to 12-30-2017.

c. Universe

Students pursuing a degree in Kinesiology and Physiatry at the Instituto Universitario de Ciencias de la Salud Fundación H.A. Barceló (Autonomous City of Buenos Aires, Argentina), at Universidad Maimónides (Autonomous City of Buenos Aires, Argentina) and at the Universidad Nacional Arturo Jauretche (Florencio Varela, Buenos Aires, Argentina).

d. Population

Composed of 255 individuals, male (5, 41, 46), students pursuing a degree in Kinesiology and Physiatry at the Instituto Universitario de Ciencias de la Salud Fundación H.A. Barceló (Autonomous City of Buenos Aires, Argentina), at Universidad Maimónides (Autonomous City of Buenos Aires, Argentina) and at the Universidad Nacional Arturo Jauretche (Florencio Varela, Buenos Aires, Argentina).

e. Sample

Composed of 30 individuals according to the sample size estimate.

f. Sample size

To determine the required sample size, a pilot test was carried out prior to the study, in which the 3 types of electrical stimulation were randomly applied to 5 subjects. In order to estimate the variability of the sample, the global standard deviation of the 15 measurements was considered (SD=19.58%). A sample size for a Two-tailed T-Test was estimated, assuming an alpha error of 0.05, a power of 0.8 and a delta of 10%. For a crossover design only 1/2 of the calculated sample size is required, since the same subject contributes to all 3 groups. This results in a sample size of 30 subjects (47). The distribution coefficient was 1:1. (48)

g. Sampling:

Consecutive non-probability.

h. Criteria

a. Inclusion: Available, healthy, male volunteers between 18 and 30 years of age, with right-dominant lower limb, who are physically active (9, 41).

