- b. Exclusion:** Having a right-dominant lower limb injury, skin lesions in the quadriceps area, having a pacemaker, cardiovascular or neurological diseases (18, 25). Subjects who have exercised 72 hours before the protocol (49, 50).
- c. Elimination:** Missing one or both appointments for evaluation, the patient's own decision to abandon the protocol while it is being carried out, intolerance to the procedure (51).

i. Randomization:

In order to minimize the potential bias of the order in which interventions are initiated (e.g., the effect of fatigue), the randomization sequence was generated prior to starting work (9, 23, 25, 52). The number 2 generator, available at <http://www.randomization.com/>, was used for situations where subjects must receive all interventions in random order, with balanced permutations, forming 5 x 6 blocks for the three currents of interest (53). The results of said distribution were as follows:

1. Aussie - RBS - Neo-Russian.
2. RBS - Neo-Russian – Aussie.
3. Aussie - Neo-Russian - RBS.
4. RBS – Aussie - Neo-Russian.
5. RBS - Neo-Russian – Aussie.
6. Aussie - RBS - Neo-Russian.
7. Aussie - Neo-Russian - RBS.
8. Aussie - Neo-Russian - RBS.
9. Neo-Russian – Aussie - RBS.
10. Neo-Russian – Aussie - RBS.
11. Aussie - RBS - Neo-Russian.
12. Neo-Russian – Aussie - RBS.
13. Neo-Russian - RBS – Aussie.
14. Aussie - Neo-Russian - RBS.
15. Neo-Russian - RBS – Aussie.
16. Neo-Russian - RBS – Aussie.
17. Aussie - RBS - Neo-Russian.
18. RBS - Aussie - Neo-Russian.
19. RBS - Aussie - Neo-Russian.
20. Aussie - RBS - Neo-Russian.

21. Neo-Russian – Aussie - RBS.
22. Neo-Russian - RBS – Aussie.
23. Neo-Russian - RBS – Aussie.
24. Neo-Russian – Aussie - RBS.
25. RBS - Aussie - Neo-Russian.
26. RBS - Neo-Russian – Aussie.
27. Aussie - Neo-Russian - RBS.
28. RBS - Aussie - Neo-Russian.
29. RBS - Neo-Russian – Aussie.
30. RBS - Neo-Russian – Aussie.

j. Blinding

The subject was blindfolded so that he would not watch the procedure. The study subject did not know the type of current applied and the operator was alien to the work and unaware of the hypothesis. The database was coded in order to conceal the interventions from the statistical analyst (25, 45).

k. Ethical aspects

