cotton soaked in alcohol. To detect the points, a Globus brand 600 Pro model equipment was used, in which an ad hoc program was executed, with continuous emission at 5 Hz, 200 us. In order to locate the motor point of the internal vastus, a self-adhesive dispersive electrode of 2" x 4" (5.08 x 10.16 cm) was placed on the proximal third of the right thigh, to then search for it with the active electrode – metal strut-type, wrapped with cotton wool soaked in tap water and covered with conductive gel- until determining the point of greatest contraction at the same intensity. For the motor point of the anterior rectus, a self-adhesive dispersive electrode was placed on the motor point of the internal vastus of the right thigh, to then search for it with the active electrode, -metal strut-type, wrapped with cotton wool soaked in tap water and covered with a conductive gel- until determining the point of greatest contraction at the same intensity.

Once these points were marked, unused self-adhesive electrodes -Pro-Patch® brand, model ProM-030, 2" x 4" (5.08 x 10.16 cm) 2, 57)- were placed on them (52, 57). Two electrodes were used for each patient.

d. Measuring MEIC

After measuring the MVIC, the subject was allowed to rest for 120 seconds (while searching for motor points), to then perform the MEIC assessment with all three types of electrical currents, which were applied in random order so that the effects of one current would not influence the results of the next (23, 25). The randomization sequence is the one mentioned above, generated through www.randomization.com (53).

The same isometric dynamometer was used, positioning the subject as indicated above. (5, 9, 12, 23, 26, 31, 37-40).

The patient was asked not to make any voluntary contraction or collaborate in any way, but just let the electrical stimulation generate the contraction (20).

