With each type of current, the intensity was increased until it reached the maximum tolerable by the subject, which situation was communicated to the operator (23, 25, 32, 52). Upon reaching said intensity, it was noted down accordingly, and then 3 contractions of 3 seconds duration were measured by isometric dynamometry, with a 120-second pause between them. Once the 3 contractions with the first current were measured, the second and then the third type of electro-stimulation followed, in the order as randomly determined (9, 23, 25, 52). An interval of 120 seconds was also taken between the determinations of the MEIC with each current, in order to minimize fatigue (9). The best of the 3 repetitions was considered (9, 23, 31, 52).

Whenever the third one was the best, additional measurements were taken until a decrease in torque was obtained in order to determine the maximum (56).

Work and rest times were controlled by a chronometer and also by the dynamometer software. The best of the three contractions and, when necessary, the request for additional repetitions to obtain the best one, was automatically determined by the software, which also served to store the data that was later transferred to an Excel 2016 table.

The following parameters were used to perform the MEIC tests (Table 1):

VARIABLE	NEO-RUSSIAN	AUSSIE	RBS
Emission mode	Synchronous	Synchronous	Synchronous
Waveform	Rectangular biphasic symmetrical	Sinusoidal	Rectangular biphasic symmetrical
Carrier frequency	2500 Hz	1000 Hz	-
Phase duration	200 us	500 us	200 us
Pulse width	400 us	1000 us	400 us
Modulation frequency	50 Hz	50 Hz	50 Hz
Duty cycle	50 %	20 %	-
Burst duration	10 ms.	4 ms.	-
Ramp-up	1 sec.	1 sec.	1 sec.
On time	3 sec.	3 sec.	3 sec.
Ramp-down	1 sec.	1 sec.	1 sec.
Rest time	120 sec.	120 sec.	120 sec.

Table 1: Parameters for electrical stimulation during MEIC measurement.

e. Normalizing MEIC data

In order to normalize the data, MEIC will be expressed as percentage of MVIC (% MVIC) (17, 20, 23, 52, 58). The calculation was done in an Excel 2016 table. The formula was the following:

$$\% \text{ MVIC} = (\text{MEIC} / \text{MVIC}) \times 100$$

f. Determining tolerance to each type of electrical stimulation

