To meet the specific objectives in 1.2, 1.4 and 1.6, an analysis of the variance of a repeated measurement factor was performed in order to determine the effect of three wave types (Aussie, NR and RBS) on the %MVIC, tolerance level and fatigue. Independent analyses were performed for each outcome variable. Bonferroni correction was applied for the *a posteriori* analyses, as appropriate. Results were expressed as mean difference and their respective 95% CI. The assumption of normality was evaluated using the Shapiro-Wilk test. The presence of outliers was determined by visual inspection of the box charts. The sphericity assumption was evaluated by means of the Mauchly test. When it was not possible to apply the parametric ANOVA test, the non-parametric Friedman test and the Wilcoxon test for Bonferroni-corrected samples were used for multiple comparisons.

To meet the specific objective in 1.2, it was analyzed which current shows the highest value of %MVIC (%MVIC-Neo-Russian vs. %MVIC-Aussie vs. %MVIC-RBS).

In order to comply with the specific objective in 1.4, it was analyzed to which of the currents the subjects referred a lower VAS value (VAS-Neo-Russian vs. VAS-Aussie vs. VAS-RBS) and which of the currents obtained a better ratio, calculated by using the formula mentioned above (Ratio-Neo-Russian vs. Ratio-Aussie vs. Ratio-RBS).

To meet the specific objective in 1.6, a comparison was made considering the number of repetitions $\leq 50\%$ of the initial value between the 3 different waves. No assumption of normality was made at any of the levels as assessed by the Shapiro-Wilk test ($p < 0.001$) for which the Friedman test was used for related samples. For post hoc comparisons the Wilcoxon Test for related samples was used with Bonferroni correction for multiple comparisons ($R \leq 50\%$ -Neo-Russian vs. $R \leq 50\%$ -Aussie vs. $R \leq 50\%$ -RBS). In addition, a comparison was made between %MVIC-F₁ vs. %MVIC -F₂₁ using the Wilcoxon Test for paired samples.

To compare fatigue rates between AU, RS and RBS groups, the Friedman non-parametric test was used with the Wilcoxon test for post hoc comparisons. Bonferroni correction was applied for post-hoc comparisons.

SOURCES AND INSTRUMENTS

- Notebook with Windows, Microsoft Office 2016 package, SPSS 22, Endnote X7.
- Owon PC-based oscilloscope, model VDS2062 60MHz and 100MHz bandwidth.

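### The parametric comparisons of currents omit a period term: no bias with the balanced list, but wider intervals and conservative tests if responses drift over the session (low severity)

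*Combined protocol and SAP*

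**What the plan says.** Section i (Randomization) gives the reason for ordering the currents at random: "In order to minimize the potential bias of the order in which interventions are initiated (e.g., the effect of fatigue". It prints 30 orders. Section l.d (Measuring MEIC) ties that list to the force session: "The randomization sequence is the one mentioned above". All three currents are then given in the same session: "the second and then the third type of electro-stimulation followed, in the order as randomly determined". The spacing is also stated: "An interval of 120 seconds was also taken between the determinations of the MEIC with each current, in order to minimize fatigue".

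Section n (Statistical processing of data) plans the comparison: "an analysis of the variance of a repeated measurement factor was performed in order to determine the effect of three wave types". Post hoc tests are Bonferroni-corrected, results are mean differences with 95% intervals, and sphericity is checked. Period, order and sequence do not appear in any model. If the parametric test cannot be used, the fallback is Friedman and Wilcoxon.

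**The concern.** The plan treats order as a real threat, balances the design for it and prints each subject's sequence, but the analysis makes no explicit use of that information. If force, discomfort or their ratio drifts from the first to the third current, the drift is known, removable variation. With current as the only factor it is counted as random error. A true difference between currents then becomes harder to detect, and its interval is wider than the data require.

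A second, smaller issue arises if subjects are eliminated. The criteria in section h.c begin with "Missing one or both appointments for evaluation" and also cover withdrawal and intolerance. Losses break the balance, and drift can then leak into the differences between currents.

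The point is limited to %MVIC, VAS and ratio when analysed parametrically. It does not extend to the fatigue count or the fatigue index. Those use rank tests, each run is scaled to its own first contraction, and section l.g does not say that the printed list governed the fatigue session.

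**Working it through.** **Inputs from the documents.** N = 30, delta = 10, two-sided alpha 0.05 and power 0.8 (section f). SD = 19.58, described there as "the global standard deviation of the 15 measurements was considered (SD=19.58"%). Three Bonferroni pairs (section n).

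**Assumptions not in the documents.** The SD applies to %MVIC. The within-subject correlation is 0.5. Current means are 0/5/10. Drift is linear, d %MVIC points per period.

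**The plan's own figure.** 2 x (1.960 + 0.842)^2 x 19.58^2 / 10^2 = 60.2 per group. Half of that is 30.1, which agrees with the stated 30.

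**Balance of the printed list (line numbers).**
- Aussie, RBS, Neo-Russian: 1, 6, 11, 17, 20
- Aussie, Neo-Russian, RBS: 3, 7, 8, 14, 27
- RBS, Neo-Russian, Aussie: 2, 5, 26, 29, 30
- RBS, Aussie, Neo-Russian: 4, 18, 19, 25, 28
- Neo-Russian, Aussie, RBS: 9, 10, 12, 21, 24
- Neo-Russian, RBS, Aussie: 13, 15, 16, 22, 23

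There are six orders of five, so each current occurs 10 times in each period. An additive period effect cancels exactly from every difference between currents.

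**Time separation.** From section l.d and Table 1, the third current starts at least 2 x (3 x 5 s + 2 x 120 s + 120 s) = 750 s = 12.5 minutes and six measured contractions after the first. Time to set the intensity comes on top.

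**Where the drift goes.** Period effects of -d, 0 and +d add 30 x 2d^2 = 60d^2 to the residual sum of squares. For a paired difference, the position gaps squared sum to 5 x (1+1+1+1+4+4) = 60, so its expected sample variance rises by 60d^2/29.

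**Paired interval.** The variance of a difference is 2 x 19.58^2 x (1 - 0.5) = 383.4.
- d = 0, no period term: 2.541 x sqrt(383.4/30) = 9.08 (29 df).
- With period term, any d: 2.552 x sqrt(383.4/30) = 9.12 (27 df).
- d = 5, no period term: 2.541 x sqrt((383.4 + 51.7)/30) = 9.68.

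**ANOVA power with period.** The noncentrality is 30 x 50 / 191.7 = 7.8 on 2 and 56 df, which gives 0.68. Values without period at d > 0 were computed from simulated normal and chi-square components and checked by simulating trials on the printed list.

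| d | ANOVA type I error, no period | ANOVA power, without / with | Paired half-width, without / with | Power of one Bonferroni contrast for 10 points, without / with |
|---|---|---|---|---|
| 0 | 0.050 | 0.68 / 0.68 | 9.08 / 9.12 | 0.60 / 0.60 |
| 2 | 0.047 | 0.67 / 0.68 | 9.18 / 9.12 | 0.60 / 0.60 |
| 3 | 0.044 | 0.66 / 0.68 | 9.30 / 9.12 | 0.58 / 0.60 |
| 5 | 0.034 | 0.62 / 0.68 | 9.68 / 9.12 | 0.54 / 0.60 |
| 10 | 0.011 | 0.45 / 0.68 | 11.27 / 9.12 | 0.38 / 0.60 |

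With the period term the ANOVA type I error is 0.05 throughout.

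**Other correlations, d = 5.** ANOVA power without / with period is 0.48 / 0.53 (correlation 0.3), 0.84 / 0.89 (0.7) and 0.95 / 0.98 (0.8).

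**Break-even.** The paired adjustment pays once 60d^2/29 exceeds 383.4 x ((2.552/2.541)^2 - 1) = 3.3, that is, d of about 1.3 (1.5 at correlation 0.3, 0.8 at 0.8).

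**Lost subjects.** Without a period term, the largest bias in one difference is 2d/29 = 0.07d, 4d/28 = 0.14d and 6d/27 = 0.22d for one, two and three losses. At d = 5 that is 0.34, 0.71 and 1.11 points.

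**The case against.** The strongest reply is that nothing here is an error. The balanced list is itself the defence against order effects, and the simple ANOVA relies on it to stay unbiased. The 120-second rests are meant to keep drift small. The documents give neither a drift nor a within-subject correlation, and up to d = 3 the loss is about 2 power points. The striking figures need d = 10, a 20-point shift across the session or twice the planned delta, which nothing in the documents supports. All of this stands, and it is why the point is rated low.

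Four further points also stand as limits:
- Only %MVIC is quantified. VAS is bounded and the ratio divides by it, so either may go to the rank tests, where this point does not apply.
- Section l.d says the currents "which were applied in random order so that the effects of one current would not influence the results of the next". That is carry-over, and a period term does not correct carry-over that differs by current.
- The number of eliminated subjects is not given, so the loss bias is only a bound.
- Section n is in the past tense and already reports a normality result, so a changed model may have to be labelled as added after the analysis began.

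None of this shows that the period term is harmful or expensive, or that the plan contains one.

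**Conclusion.** The point holds as a low-severity efficiency matter. The parametric comparisons of %MVIC, VAS and ratio leave out a factor that the design controlled and recorded. With all 30 subjects there is no bias from additive drift, and the planned tests are valid, at worst conservative. Under the assumptions above, the loss is negligible to modest for d up to 3, and about 6 power points and 0.56 points of half-width (9.68 - 9.12) at d = 5. With no drift there is nothing to gain. The absence of bias rests on additive period effects and a complete list.

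**What to change.** For %MVIC, VAS and ratio, when analysed parametrically, adjust the Bonferroni pairwise contrasts for period. The simplest form is enough: for each pair of currents, regress the within-subject difference on an intercept and the two period-difference columns, and read the adjusted difference from the intercept (27 error df).

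An alternative is a linear mixed model with period and current as fixed effects and an unstructured within-subject covariance by current. Conclusions should then come from its Bonferroni contrasts, because its overall F was slightly liberal in simulation at this N (0.054 to 0.058). Neither option relies on sphericity. Pooled-error contrasts from a plain subject, period and current ANOVA do, and should not be used unless sphericity holds. If results have already been seen, report the adjusted analysis with its timing stated.

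Leave the Friedman and Wilcoxon analyses, including the fatigue count and fatigue index, as planned.

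The cost is a change of SAP wording and a short re-run, with no new data provided each subject's line in the list was kept. Two error degrees of freedom are spent. With no drift, at correlation 0.5, a paired half-width grows by 0.04 points and power for a 10-point difference falls from 0.604 to 0.600.

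### Plain Bonferroni over three currents is valid but needlessly conservative; Shaffer's step procedure would add about 9 points of power per true pair at the plan's own sizing inputs

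*Combined protocol and SAP*

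**What the plan says.** Materials and Methods, section n (Statistical processing of data), describes a separate analysis for each outcome: "an analysis of the variance of a repeated measurement factor was performed in order to determine the effect of three wave types", with Friedman's test where the parametric assumptions fail. Paired comparisons follow, and "Bonferroni correction was applied for post-hoc comparisons". With three currents there are three pairs, so the working level is 0.05/3 = 0.0167 per pair. The section calls these comparisons post hoc, but nowhere says that they are made only after a significant overall test. It adds: "Results were expressed as mean difference and their respective 95% CI". It does not say whether those intervals are adjusted.

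Objectives 1.2, 1.4 and 1.6 ask which current induces most force, is least unpleasant and tires the muscle least. The paired comparisons are what answers these questions.

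Section f (Sample size) sets the inputs: "A sample size for a Two-tailed T-Test was estimated, assuming an alpha error of 0.05, a power of 0.8 and a delta of 10" percent. It takes the SD of the 15 pilot measurements as 19.58%, and then: "For a crossover design only 1/2 of the calculated sample size is required, since the same subject contributes to all 3 groups". The result is 30 subjects.

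**The concern.** Bonferroni treats the three paired hypotheses as if any combination could be true or false. With three currents that is not so. If A and B differ, C cannot equal both of them. After one pair has been correctly declared different, only one true null can remain, and it can be tested at the full 0.05. Bonferroni keeps all three at 0.0167 throughout.

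What is at stake is power. The sample is fixed at 30 and was sized at 0.05 per comparison, while the comparisons that answer the objectives run at a third of that level.

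**Working it through.** **Inputs.** From section f: two-sided alpha 0.05, power 0.80, delta 10 and SD 19.58 (read here as percentage points of %MVIC), 30 subjects. From section n: three pairs per outcome, 0.0167 each. Not in the documents: the correlation between a subject's responses to two currents.

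**1. The plan's own figure.** Per-group size for two independent means:

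n = 2 × (1.960 + 0.842)² × 19.58² / 10² = 2 × 7.849 × 383.4 / 100 = 60.2, rounded up to 61.

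Half of this is 30.1 to 30.5, which agrees with the stated 30.

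**2. The correlation this implies.** A paired comparison has SD of differences = 19.58 × √(2(1 − ρ)) and needs (1 − ρ) times the per-group n. Halving therefore amounts to ρ = 0.5, where the SD of differences is 19.58 × √1 = 19.58. This is an inference from the halving. At ρ = 0.75 the SD of differences would be 19.58 × √0.5 = 13.8.

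**3. One pair at the Bonferroni level.** At ρ = 0.5 and n = 30, single-pair power falls from 80% to 66% (normal approximation), or from 77% to 60% (paired t), when the level goes from 0.05 to 0.0167. Holding 80% at 0.0167 would take (2.394 + 0.842)² × 383.4 / 100 = 10.47 × 3.834 = 40.1 subjects, or 40.5 if the per-group size is rounded up before halving.

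**4. Shaffer's procedure for three treatments.** Test the smallest p-value at 0.05/3. If it is significant, test the other two at 0.05.
- All three nulls true: a false claim needs the smallest p-value below 0.0167. This is the same event as for Bonferroni, with simulated error 4.5%.
- Exactly one null true: it can only be rejected with p < 0.05, so the error is at most 5%.
- Exactly two nulls true: impossible for three means.

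Every pair that Bonferroni rejects is also rejected here.

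**5. Power by simulation** (n = 30, normal data, paired t-tests, equal variances, ρ = 0.5, 60,000 runs):

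| True means | Quantity | Bonferroni | Shaffer | Gain |
|---|---|---|---|---|
| 0, 0, 10 | each true pair | 0.60 | 0.69 | 0.09 |
| 0, 0, 10 | separate current from both others | 0.44 | 0.61 | 0.17 |
| 0, 10, 20 | best current from both others | 0.60 | 0.77 | 0.17 |
| 0, 5, 10 | 10-point pair | 0.60 | 0.63 | 0.03 |
| 0, 5, 10 | each 5-point pair | 0.14 | 0.24 | 0.10 |

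**6. Sensitivity.** At ρ = 0.75 with one current apart, Bonferroni already has power of about 0.91 per true pair, and the gain is about 4 to 5 points.

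**7. The alternative, an overall test as gate and then pairs at 0.05.** At ρ = 0.5 with one current apart it gives 0.72 per pair and 0.64 for both pairs. Its family-wise error is about 5% with equal variances. Without the gate, pairs at 0.05 give about 12.4%. With unequal variances and an uncorrected F test, the gated procedure gives 5.7 to 6.4% in the cases tried; with a Greenhouse-Geisser correction it gives about 5%.

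**The case against.** The strongest reply is that nothing here is wrong. Bonferroni controls the error rate, fits in one line and needs no assumption about the overall test. That stands: the point concerns efficiency only.

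A reader might go further and infer that Bonferroni is redundant because the overall test already protects the pairs. The text does not support that. Section n never makes the overall test a condition for the paired tests, so as written Bonferroni is the only stated family-wise protection. Section n also names Mauchly's test without naming a correction, so the F test could not be relied on as a gate under unequal variances. Shaffer's procedure with paired t-tests needs neither the gate nor sphericity.

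A reader might also infer a loss of 13 to 26 points throughout. The 26 is 0.56 − 0.30, the power to find all three differences when the currents lie at 0, 10 and 20. That spread is twice the plan's delta, and the objectives ask for the best current, not a full ranking. The lower figure compares Bonferroni with the gated test at one assumed correlation.

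Nor do the intervals contradict the tests. The sentence on 95% intervals directly follows one on Bonferroni, so adjusted intervals are a natural reading. The text only leaves this open.

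Finally, section n is in the past tense and reports a Shapiro-Wilk result, so some data had been examined. That limits when the change can be made.

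**Conclusion.** The concern holds as a cheap gain in efficiency and not as a fault in error control. At the plan's sizing inputs and an assumed correlation of about 0.5, Shaffer's procedure adds about 9 points of power per true pair when one current stands apart, and about 17 points for separating the best current from both others. At correlation 0.75 the gain is about 4 to 5 points per pair.

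These figures assume normal data with equal variances and apply to the outcome for which delta 10 and SD 19.58 are meant. The documents give no effect sizes for VAS, ratio or fatigue, so no gain in points can be stated for objectives 1.4 and 1.6. Neither procedure addresses multiplicity across outcomes.

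**What to change.** In section n, replace the Bonferroni sentences by wording such as: *Within each outcome, the smallest of the three pairwise p-values is compared with 0.05/3. If it is significant, each of the other two is compared with 0.05; if not, no pair is declared different (Shaffer's procedure).*

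Alternatively, test pairs at 0.05 only if the overall test is significant at 0.05. That gate must then be written out, and the ANOVA must use a Greenhouse-Geisser correction. On the Friedman and Wilcoxon route, the closure argument assumes exchangeability of the currents under the null. Shaffer's step on Wilcoxon p-values likewise needs the nulls to be read so that two equalities imply the third.

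State also whether the 95% intervals are per comparison or Bonferroni-simultaneous.

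The cost is a sentence or two and no subjects. The downside is in the intervals: three ordinary 95% intervals cover jointly only about 87% (about 95.5% with Bonferroni), and they may not match the test decisions. The change must be fixed before unblinded results are seen. If that is no longer possible, keep Bonferroni as planned and report Shaffer's procedure as a labelled supplementary analysis.
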